Furosemide for Accelerated Recovery of Blood Pressure Postpartum: a randomized controlled trial (FoR BP trial)

A randomized, double-blind, placebo-controlled single center investigation of furosemide's effect on postpartum blood pressure control in pregnancies affected by hypertensive disorders of pregnancy

Protocol date: July 19, 2018

NCT#03556761

Furosemide for Accelerated Recovery of Blood Pressure Postpartum: a randomized controlled trial (FoR BP trial)

A randomized, double-blind, placebo-controlled single center investigation of furosemide's effect on postpartum blood pressure control in pregnancies affected by hypertensive disorders of pregnancy

Principal Investigator: [name], MSCE

Assistant Professor

Division of Maternal Fetal Medicine

Department of Obstetrics and Gynecology

[name]

[name]

Sub-Investigator(s): [name] [name]

Clinical Fellow

Division of Maternal Fetal Medicine

Department of Obstetrics and Gynecology,

Study Drug/Study Device: Furosemide (Lasix)

LIST OF ABBREVIATIONS

AE Adverse Event

CTCAE Common Terminology Criteria for Adverse Events

DSMB Data and Safety Monitoring Board

gHTN Gestational hypertension H&P History & Physical Exam

HRPP Human Research Protections Program
HDP Hypertensive disorders of pregnancy

[figure not shown]
HTN Hypertension IV (or iv) Intravenously

PI Principal Investigator
PO per os/by mouth/orally
PPHTN Postpartum hypertension

PR Partial Response

SAE Serious Adverse Event

STUDY SCHEMA

STUDY SUMMARY

Title	Furosemide for Accelerated Recovery of Blood Pressure Postpartum: a randomized controlled trial			
Short Title	FoR BP trial			
Methodology	Double blind, randomized, placebo control design			
Study Duration	20 months			
Study Center(s)	Single-center			
Objectives	To investigate the impact of a short course of furosemide on postpartublood pressure recovery in women with hypertensive disorders of pregnancy (HDP).			
Number of Subjects	385			
Diagnosis and Main Inclusion Criteria	Clinical disease state under study: hypertensive disorder of pregnancy, postpartum with delivery >20 weeks EGA, diagnosis of HDP antepartum, intrapartum and up to within 1 day of delivery			
Study Product(s), Dose, Route, Regimen	Furosemide (Lasix), 20mg, PO, daily			
Duration of administration	5 days			
Reference therapy	Placebo			
Statistical Methodology	Intention to treat analysis, chi-square tests for categorical variables, two-sample t-test for continuous variables			

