2.3.2 Secondary endpoints

- 2.3.2.1 Number of readmission/ ER visit that is hypertension related
- **2.3.2.2** Frequency of severe hypertension (SBP>160mmHg or DBP>110mmHg)
- **2.3.2.3** Number of days required until blood pressure resolution (<140/90 for 2 days)
- 2.3.2.4 Postpartum length of stay
- 2.3.2.5 Complications during hospitalization related to hypertensive disorders of pregnancy (acute pulmonary edema, acute kidney injury, disseminated intravascular coagulation, stroke or myocardial infarction, eclampsia, ICU stay, maternal death)
- **2.3.2.6** Adverse effects secondary to furosemide

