5 STUDY PROCEDURES

5.1 Screening for Recruitment and Recruitment Process

The labor and delivery board and patient list will be screened daily to identify eligible patients. Women identified as having a hypertensive disorder of pregnancy will be invited to participate in the study and written informed consent will be obtained from those who choose to participate in the postpartum period. All screening procedures must be performed within 24 hours of delivery. The screening procedures include:

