5.2 Randomization

If the patient is eligible, after informed consent the patient will be randomized by IDS. We plan to randomize through a computer generated sequence in blocks of 4 and stratify randomization blocks by whether severe features are present or not (ie., gestational hypertension and pre-eclampsia without severe features vs. pre-eclampsia with severe features). IDS will then dispense the furosemide or placebo accordingly.

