Patients in both groups will undergo similar postpartum surveillance, including blood pressure and pulse assessment every 4 hours and urinary output measurements while hospitalized. Proper treatment for elevated blood pressures will be initiated immediately as soon as the elevated blood pressures are recognized, and will not be delayed for any study purposes including study drug administration. For this study, antihypertensive therapy will be initiated for persistently elevated postpartum blood pressures (BP) of ≥ 150 systolic or >100 mg Hg diastolic with 5 mg of amlodipine PO. Persistent severe range blood pressures (BP >160 mm Hg systolic or >110 mm Hg diastolic) will be treated with IV antihypertensives if needed, as well as 10 mg of amlodipine PO. If further antihypertensive medications are needed to maintain blood pressures <150/100, these will be per the discretion of the clinical staff in both arms. All physicians and clinical staff in Labor and Delivery as well the postpartum unit will be educated extensively to avoid diuretic antihypertensive medications unless deemed medically necessary. Furthermore, diagnostic and laboratory tests will be per the discretion of the clinical staff in both arms as well. Routinely, all patients undergoing cesarean section remain hospitalized for at least 3 days and all patients with preeclampsia with severe features are kept in the hospital for 3 days (per the recommendations of the ACOG Task Force on Hypertension in Pregnancy). 10 All patients will be followed at for 10 days after discharge as detailed below. Being enrolled in the study will not change the patient's clinical care at any time. Physicians, staff, and patients will be blinded to the intervention administered, unless a break in blinding is required for medical intervention of adverse effects.

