9.2 Data Analyses Plans

To account for the multiple measurements per patient, we will employ repeated measure regression techniques. Measures of relative risk will include 95% confidence intervals. Descriptive statistics will be presented as mean with standard deviation, median with interquartile range, or proportion with 95% confidence interval based on data type and distribution. Comparisons between groups will be performed using a Chi-square or Fisher's exact test for categorical variables and parametric or non-parametric tests for continuous variables, as appropriate. Bivariable analysis will be used to determine variables (risk factors) that are independently associated with PPHTN. Intention-to-treat analyses will be conducted such that all patients with available follow-up measures will be included in the analysis. Blood-pressure measurements after randomization will be compared between groups with the use of a mixed-effects logistic-regression model, which will account for participants having different numbers of observations over a varying time span. Statistical analyses were conducted in SAS, version 9.4 (SAS Institute, Cary, NC). Two-tailed P values of <0.05 will be considered statistically significant.

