10.2 Collection of data

We will record data on each patient regarding their demographics, obstetrical and medical history, labor and delivery admission and any readmission information within 6 weeks postpartum.

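### Length of stay is compared without covariates although usual discharge practice ties it to cesarean delivery and severe features; adjusting is a free, possibly small, gain in precision

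*Combined protocol and SAP*

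**What the plan says.** Section 2.3.2.4 lists "Postpartum length of stay" as a secondary endpoint. Nothing in the documents names an analysis for it, so the general rules apply. The Statistical Methodology row of the study summary gives "two-sample t-test for continuous variables". Section 9.2 is looser: "parametric or non-parametric tests for continuous variables, as appropriate". Neither mentions a covariate or the stratification factor. The regression models in 9.2 are for repeated measurements and blood pressure, and a woman has only one length of stay.

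Section 5.3 describes routine practice. On mode of delivery it states: "all patients undergoing cesarean section remain hospitalized for at least 3 days". On disease severity, the same sentence adds a second rule: "all patients with preeclampsia with severe features are kept in the hospital for 3 days".

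Both factors are settled before allocation. Section 5.1 says "written informed consent will be obtained from those who choose to participate in the postpartum period", and section 5.2 places randomisation after consent, so mode of delivery is already fixed. Section 5.2 also plans to "stratify randomization blocks by whether severe features are present or not". Mode of delivery is not a stratum. Section 10.2 covers "labor and delivery admission and any readmission information within 6 weeks postpartum", without naming mode of delivery.

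**The concern.** The protocol itself identifies two determinants of stay, stratifies on one of them, and leaves both out of the comparison. Days in hospital that follow from usual practice, and have nothing to do with furosemide, then sit in the residual variance. Chance differences between arms in the cesarean share also stay in the estimate. At stake is how precisely the trial can say whether furosemide shortens the stay. The primary composite is not affected.

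**Working it through.** **Plan's own figure.** There is none for length of stay: no standard deviation, target effect or power. Section 9.1 sizes the trial on blood pressure only. I take its 175 as per arm, since 2 × 175 × 1.10 = 385. The standard-error ratios below do not depend on this number.

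**Inputs.** From the documents: 3 days after cesarean or with severe features (5.3), 1:1 allocation (1.2), two-sided 5% (9.2). Assumed, because the documents are silent: cesarean share c = 25–50%, severe-features share s = 30–50%, stay longer by d = 0.5 or 1.0 day with either factor, standard deviation within groups σ = 0.75, 1.0 or 1.5 days.

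**Formulas.**
- Share of women with either factor: p = 1 − (1 − c)(1 − s).
- Variance explained: R² = d²p(1 − p) / [d²p(1 − p) + σ²].
- Unadjusted over adjusted standard error: 1/√(1 − R²).
- Unadjusted power for an effect with 80% power adjusted: Φ(2.80/ratio − 1.96).

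**Results.**

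| Case | c | s | d | σ | p(1 − p) | R² | SE ratio | Power, unadjusted |
|---|---|---|---|---|---|---|---|---|
| Smallest | 50% | 50% | 0.5 | 1.5 | 0.1875 | 0.020 | 1.01 | 79% |
| Middle | 35% | 40% | 1.0 | 1.0 | 0.2379 | 0.192 | 1.11 | 71% |
| Largest | 25% | 30% | 1.0 | 0.75 | 0.2494 | 0.307 | 1.20 | 65% |

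In patients, 1/(1 − R²) runs from 1.02 to 1.44.

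**Simulation.** 8,000 trials per scenario, 175 per arm, blocks of 4 stratified by severe features, c = 35%, s = 40%; t-test against a linear model with both factors and their product.

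| d | σ | SE, t-test | SE, adjusted | Power, t-test | Power, adjusted | Type I error, t-test |
|---|---|---|---|---|---|---|
| 1.0 | 1.0 | 0.119 | 0.107 | 72% | 80% | 4.2% |
| 1.0 | 0.75 | 0.096 | 0.080 | 66% | 79% | 3.4% |
| 0.5 | 1.0 | 0.110 | 0.107 | 77% | 79% | 4.6% |
| 1.0 | 1.5 | 0.169 | 0.161 | 76% | 79% | 4.5% |

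Adjusted type I error was 4.8–5.3%. The t-test falls below 5% because stratification balances severe features while the t-test still counts that variation as noise. With 8,000 runs the simulation error is √(0.05 × 0.95/8,000) = 0.24 points, so 4.5% and 4.6% are only marginally below 5%.

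**Sensitivity to the usual stay without either factor.** Now let stay be a minimum plus an exponential extra stay of mean m, so σ = m, again with c = 35% and s = 40%.

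| Minimum without either factor | R² at m = 0.5 | R² at m = 1.0 | R² at m = 1.5 |
|---|---|---|---|
| 2 days (d = 1) | 0.49 | 0.19 | 0.10 |
| 2.5 days (d = 0.5) | 0.19 | 0.06 | 0.03 |
| 3 days (d = 0) | 0 | 0 | 0 |

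The top-left cell gives a ratio of 1/√(1 − 0.49) = 1.40, beyond the grid above. It needs both a full day's difference and stays that cluster tightly above the minimum.

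**Stratum or mode of delivery?** With c = 35% and s = 40%, the part of p(1 − p) due to mode of delivery within strata is 0.60 × 0.35 × 0.65 = 0.1365. As a share, 0.1365/0.2379 = 57%. Adjusting for the stratum alone would therefore recover less than half of the rule-driven variance.

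**Chance imbalance.** With about 192 per arm and c = 35%, the difference in cesarean share has standard deviation √(0.35 × 0.65 × 2/192) = 0.049. Times a 1-day difference, that is about 0.05 day, or 1.2 hours.

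**The case against.** The strongest reply is that nothing here is wrong. A reader might infer that the unadjusted test is biased or gives too many false positives. It does neither: randomisation makes it unbiased, and under this stratified design it errs, if at all, on the conservative side. That part of the objection stands in full.

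A reader might also take the t-test as settled for this endpoint. Only the one-line summary entry says so; section 9.2 leaves a non-parametric test open. This stands too, but either route is unadjusted.

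Nor do the documents show that care rules fix much of the variation in stay. Section 5.3 describes what happens routinely, and the cesarean figure is a minimum. No passage gives the usual stay of women with neither factor. Section 1.1 mentions guidance to monitor blood pressure in hospital for 72 hours, without limiting it to severe disease. If these women also stay about 3 days, adjustment gains nothing.

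Chance imbalance in cesarean share is small, and the unadjusted standard error already allows for it, so it is not a separate harm. Finally, this is one of six secondary endpoints, with no power target.

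What the objection does not remove is that both factors are known at baseline, one of them is the stratum, and the plan uses neither.

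**Conclusion.** The point holds as a free improvement, not as the correction of an error. The planned comparison of length of stay is valid but may be less precise than it could be. The size cannot be taken from the documents. It runs from nothing (3 days for everyone), through 1% to 20% on the standard error over the assumed grid, to more only if stays vary little beyond the minimum. A claim that the power gain reaches 5 points in most situations would not be supported: it depends on a 2-day stay for women with neither factor, which the documents do not state. Severity is low.

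**What to change.** In section 9.2, prespecify for length of stay, measured in hours from delivery to discharge:
- a linear model with treatment, the severe-features stratum as recorded at randomisation, mode of delivery and the stratum-by-mode interaction, with robust standard errors;
- the adjusted mean difference with 95% confidence interval as the reported result;
- the unadjusted comparison as a sensitivity analysis, with the test named.

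Severe features that appear after randomisation should not enter the model, because they are not baseline. In section 10.2, name mode of delivery among the data collected.

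The cost is a sentence or two of wording. It needs no extra patients, visits or change in care. It also closes the open choice of test for this endpoint and avoids a post hoc decision to adjust if cesarean rates happen to differ between arms.

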1 BACKGROUND AND RATIONALE

1.1 Disease Background

Hypertensive disorders of pregnancy are recognized causes of significant maternal/fetal morbidity and mortality, accounting for approximately 18% of maternal deaths worldwide. 1 While significant research has been done on the evaluation and management of hypertension during pregnancy, studies of postpartum hypertension (PPHTN) are usually limited by their retrospective design and focus on inpatients in the immediate postpartum period (2-6 days), or patients who were readmitted due to complications related to hypertension.² Few studies have investigated the incidence and proper management of hypertension in the postpartum period. PPHTN can present either de novo, following a normotensive pregnancy, or as persistent hypertension following a pregnancy complicated by preeclampsia or other hypertensive disorders of pregnancy.^{2,3} Limited information is available on the clinical seguelae of PPHTN, but retrospective studies suggest that it can lead to death or to potentially life-threatening complications, such as cerebrovascular accidents, 4,5 seizures, 6 congestive heart failure, pulmonary edema, and renal failure. 2,7 Furthermore, in the United Kingdom, a review of maternal deaths determined that 10% were related to HDP in the postpartum period.8 Postpartum hypertension is also the cause of approximately 27% of readmissions to the hospital.9 These studies clearly show that PPHTN is associated with significant morbidity and that it is important to develop interventions that can reduce its effects.

Guidelines from national organizations such as the American College of Obstetrics and Gynecology (ACOG) recognize the growing concern with postpartum hypertension and have put forth specific guidelines on how to monitor for hypertension postpartum. This includes educating patients of signs and symptoms of pre-eclampsia, monitoring blood pressures for 72 hours in the hospital prior to discharge, and checking an ambulatory blood pressure within 10 days of delivery. However, only checking blood pressures 7 to 10 days after delivery is likely missing a significant number of patients. Several studies note that only 28 to 57% of patients PPHTN have their blood pressure normalize within 3 days^{12,13} Furthermore, data out of our own institution noted that 6% of women with HDP were readmitted within 3 to 14 days for hypertension related reasons. Therefore, interventions to improve the care of women with PPHTN are urgently needed.

1.2 Study Agent(s)/Devices Background and Associated Known Toxicities

Furosemide (Lasix) is a loop diuretic that is also a known antihypertensive. It exerts its mechanism of action by inhibiting reabsorption of sodium and chloride in the ascending loop of Henle and distal renal tubule. It also interferes with the chloride-binding cotransport system. Accordingly, this causes increased excretion of water, sodium, chloride, magnesium, and calcium. It is known to have onset of action of up to 60 minutes if given by mouth and 5 minutes if given by IV for diuresis. Duration is estimated to 6-8 hours when given orally and 2 hours when given IV. It is a hepatically metabolized medication with 91-99% protein binding (mostly albumin). Bioavailability ranges from 47-64% orally and it has a half-life of 0.5–2 hours. Excretion is through the urine with 50% of the PO version 80% of the IV version of the drug excreted within 24 hours. Significant side effects are related to the fluid and electrolyte shifts that occur with its lack of resorption of electrolytes. These include, but are not completely limited to ototoxicity, mood changes, confusion, muscle pain, palpitations, dizziness, syncope, increased thirst, fatigue, weakness, decreased appetite, dry mouth, dry eyes, upset stomach, nausea, and emesis.

Prior studies for the prevention and treatment of postpartum hypertension with furosemide had mixed results. Three trials (390 women) assessed oral furosemide (20-40 mg/day) in postpartum women with preeclampsia.³ In one study, there was a non-statistically significant trend to more rapid blood pressure reduction in the group receiving furosemide.¹⁴ The second study showed that furosemide, given postpartum, was associated with reduced systolic blood pressures only among women with severe preeclampsia.¹⁵ Meanwhile, the third study found that although furosemide was able to reduce the amount of antihypertensive medication given, no significant differences in

blood pressures were found in patients with severe preeclampsia. Given the inconclusive results and little data thus far on the use of postpartum furosemide, a recent Cochrane review concluded that more data is needed on substantive outcomes before the practice of postnatal furosemide can be recommended.

Placebo will be given to half of our enrolled patients which will be determined through randomization. All placebo will be manufactured and distributed by the Investigational Drug Service (IDS) of the University of Pennsylvania. IDS will manufacture the placebo to be similar to the furosemide pill. If necessary, IDS will add a coating shell to both the furosemide and placebo pills to ensure that all pills look similar.

1.3 Rationale

In patients with HDP, postpartum blood pressure has been shown to decrease in the first 48 hours postpartum only to then increase in days 3-6 postpartum. This phenomenon is thought to be secondary to large fluid shifts, both secondary from fluid retention during the pregnant state as well as from fluids given intrapartum. Furthermore, large volumes of sodium are also mobilized into the intravascular compartment at this time. Given the latter, furosemide, a loop diuretic that mobilizes sodium and fluid excretion has been posed as a method to prevent severe range blood pressures and their associated maternal morbidity in the postpartum period.

2 STUDY AIMS

- **2.1 AIM 1:** To compare the rate of persistently elevated blood pressures 7 days postpartum in women that receive a five day furosemide course compared to those that receive placebo
- **2.2 AIM 2:** To compare the time (days) required to achieve a resolution of elevated blood pressure.

2.3 Endpoints

2.3.1 Primary endpoint

- **2.3.1.1** Postpartum hypertension composite outcome, defined as:
 - Persistently elevated blood pressure (≥140/90) at 7 days postpartum OR
 - Additional requirement of antihypertensive agents after randomization

2.3.2 Secondary endpoints

- 2.3.2.1 Number of readmission/ ER visit that is hypertension related
- **2.3.2.2** Frequency of severe hypertension (SBP>160mmHg or DBP>110mmHg)
- **2.3.2.3** Number of days required until blood pressure resolution (<140/90 for 2 days)
- 2.3.2.4 Postpartum length of stay
- 2.3.2.5 Complications during hospitalization related to hypertensive disorders of pregnancy (acute pulmonary edema, acute kidney injury, disseminated intravascular coagulation, stroke or myocardial infarction, eclampsia, ICU stay, maternal death)
- **2.3.2.6** Adverse effects secondary to furosemide

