3.1 Inclusion Criteria

- **3.1.1** Hypertensive disorder of pregnancy diagnosed antepartum or intrapartum
 - Patients with diagnosis of preeclampsia with severe features, superimposed preeclampsia and gestational hypertension as diagnosed per ACOG guidelines¹⁰
 - Gestational hypertension
 - Two blood pressures at least 4 hours apart ≥ 140/90 with no proteinuria or other laboratory abnormalities (detailed below)
 - Pre-eclampsia with severe features and superimposed pre-eclampsia (any of the findings below)
 - Two blood pressures at least 4 hours apart ≥ 160/110 (unless patient given antihypertensive therapy before this time)
 - Thrombocytopenia (platelets <100,000/microliter)
 - Liver enzymes at least twice the normal concentration, and/or severe right upper quadrant/ epigastric pain
 - Serum creatinine > 1.1 mg/dL or a doubling of baseline serum creatinine
 - Pulmonary edema
 - New-onset cerebral or visual disturbances (headache, blurry vision)

- 3.1.2 New diagnosis of HDP within 1 day from delivery
- 3.1.3 Postpartum, delivery ≥ 20 weeks EGA
- **3.1.4** Age ≥18 years old
- **3.1.5** Have a phone with texting service and be willing to enroll in HUP's established postpartum hypertension texting program, HeartSafe Motherhood
- **3.1.6** Ability to understand and the willingness to sign a written informed consent and comply with study procedures

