3.2 Exclusion Criteria

- **3.2.1** History of allergic reaction to furosemide
- 3.2.2 High risk comorbidities for which treatment may be indicated or contraindicated: class C or higher diabetes mellitus, chronic kidney disease or baseline creatinine >1.2, cardiac disorders including cardiomyopathy, congenital heart disease, angina or coronary heart disease, rheumatic disease (lupus), sickle cell disease
- 3.2.3 Baseline labs with K <3
- 3.2.4 Use of furosemide or other diuretics antepartum or intrapartum
- **3.2.5** Use of ototoxic agents including aminoglycosides (ie, Gentamicin for >1 dose), cephalosporins (ie Ancef >1 dose),
- **3.2.6** Patient unstable for protocol per investigator's judgement

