4.2 Toxicities and Dosing Delays/Dose Modifications

Any patient who receives treatment will be evaluable for toxicity. Each patient will be assessed for the development of toxicity according to development of ototoxicity or symptomatic derangements in electrolytes as determined by symptoms and corresponding daily basic metabolic profiles. In the event of the development of either, the medication will be discontinued.

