5.1.7 Adverse event assessment

Baseline adverse events will be assessed. See section 6 for Adverse Event monitoring and reporting.

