5.3 Procedures During Treatment

After enrollment and consent, a specific order will be placed in the electronic medical record for this study's purposes. This order will alert IDS that a patient has been enrolled and the patient will be randomized accordingly. After randomization, IDS will send to the floor either 5 doses of placebo or furosemide clearly marked for the specific patient. A research coordinator will be present at this time and ensure that there are 5 doses of furosemide/placebo and that the patient's nurse is aware that the patient is enrolled in the study. The research coordinator will also ensure that the medication order is given by postpartum day 1 and ensures that the first pill is given after 6 hours from delivery. Patients in the furosemide arm will be assigned to receive oral furosemide 20 mg/day for a total of 5 consecutive days during hospitalization and after discharge. This dose of furosemide is based on prior studies,3 which have shown it to be safe with breast feeding. For those randomized to the placebo group, they will be given placebo pills for a total of 5 consecutive days. The time of initiation of first pill given will be recorded by the research coordinator. Each time a pill is given in the hospital, it will be accounted for in the medical administration record (MAR) in the EMR. Pills should be given approximately 24 hours apart, and the Epic order placed after enrollment will have this distinction.

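### Endpoint 2.3.2.5 sets no onset after randomization, so complications present before the first dose, some of them entry criteria, can be counted as outcomes

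*Combined protocol and SAP*

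**What the plan says.** Section 2.3.2.5 of the combined protocol and SAP lists as a secondary endpoint "Complications during hospitalization related to hypertensive disorders of pregnancy (acute pulmonary edema, acute kidney injury", followed by DIC, stroke or myocardial infarction, eclampsia, ICU stay and maternal death. It gives no starting point for the count and does not define acute kidney injury. The drug component of the primary endpoint (2.3.1.1) does have a starting point: "Additional requirement of antihypertensive agents after randomization".

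Section 3.1.1 lets a woman enter on severe features that include pulmonary edema and "Serum creatinine > 1.1 mg/dL or a doubling of baseline serum creatinine". Two exclusions in 3.2 bear on the same features: "chronic kidney disease or baseline creatinine >1.2" (3.2.2) and "Use of furosemide or other diuretics antepartum or intrapartum" (3.2.4).

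Sections 5.3 and 6.1 put the first dose more than 6 hours after delivery, with the order given by postpartum day 1. Section 10.2 collects data on the labor and delivery admission. Section 5.1.7 says "Baseline adverse events will be assessed", but neither it nor the analysis plan in 9.2 removes such events from 2.3.2.5.

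**The concern.** The window for 2.3.2.5 is the hospital stay, and part of that stay comes before treatment. A woman who enters because of pulmonary edema or a doubled creatinine already has a finding that could be scored as a listed complication. Eclampsia, DIC and an ICU stay have the same gap if they occur before randomization. The drug cannot change any of these events. Counting them mixes baseline status into an outcome comparison, and abstractors would have to decide case by case whether a presenting feature counts.

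Kidney injury deserves a clean count. Section 8.1 notes that loop diuretics may increase the nephrotoxicity of NSAIDs, so this is a plausible harm as well as a disease complication.

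**Working it through.** **Step 1. Can pre-dose events enter the count?**

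- *Kidney injury, if the baseline creatinine in 3.2.2 is the screening value.* Values above 1.2 mg/dL are excluded. Women above 1.1 and up to 1.2 mg/dL still enter under 3.1.1. So do women whose value doubled but stayed at or below 1.2 mg/dL, for example from 0.5 to 1.0.
- *Kidney injury, if that baseline is the value before the disease.* The exclusion then removes no acute rise at all. The protocol does not date the value.
- *Pulmonary edema.* Section 3.2.4 removes women given diuretics before or during labor, so pre-dose edema should be uncommon. It does not cover edema managed without a diuretic, or edema that arises after delivery but before randomization.
- *Timing.* Labor and at least 6 hours after delivery lie inside the admission and before the first dose.

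The overlap is narrow on some readings, but it is not closed on any.

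**Step 2. What would counting them do?** The plan gives no figure to reproduce: no rate and no power for 2.3.2.5. All rates below are assumptions.

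Inputs: n = 385/2, about 192 per arm (9.1); assumed post-dose risks pF and pP; a share x of each arm with a counted pre-dose event, equal in both arms and not overlapping with post-dose events.

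- Observed RR = (pF + x)/(pP + x).
- Observed risk difference (RD) = (pF + x) − (pP + x) = pF − pP, so it does not change.
- SE of the RD = √{[(pF + x)(1 − pF − x) + (pP + x)(1 − pP − x)]/192}; 95% CI = RD ± 1.96 SE.

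Kidney injury at 6% (furosemide) versus 2% (placebo):

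| x | RR | SE, points | RD (95% CI), points | CI width vs x = 0 |
|---|---|---|---|---|
| 0 | 6/2 = 3.0 | √[(0.0564 + 0.0196)/192] = 1.99 | 4.0 (0.1 to 7.9) | reference |
| 0.5% | 6.5/2.5 = 2.6 | √[(0.0608 + 0.0244)/192] = 2.11 | 4.0 (−0.1 to 8.1) | 6% wider |
| 2% | 8/4 = 2.0 | √[(0.0736 + 0.0384)/192] = 2.42 | 4.0 (−0.7 to 8.7) | 21% wider |

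At 4% versus 2%, the RR goes from 2.0 to 4.5/2.5 = 1.8 (x = 0.5%) or 6/4 = 1.5 (x = 2%). The interval is 8% or 28% wider.

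A benefit is diluted in the same way. If furosemide halved a complication from 5% to 2.5%, the RR of 0.50 would read 3.0/5.5 = 0.55 (x = 0.5%) or 4.5/7.0 = 0.64 (x = 2%).

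If pre-dose and later events occurred independently, the RD would be multiplied by (1 − x). The 4.0 points would become 3.98 or 3.92, which is negligible.

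**Step 3. Could the trial resolve this outcome with clean counts?** Hardly. At 6% versus 2%, exact two-sided Fisher power is 42% with x = 0, 38% with x = 0.5% and 30% with x = 2%. At 4% versus 2% it is 12% with x = 0.

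**The case against.** Trial outcomes are usually read as post-enrolment events, baseline adverse events are assessed separately, and investigator judgement (3.2.6) may keep unstable women out. The text permits pre-dose counting but does not direct it. This is fair, and it is why the point is about wording. The drug component of the primary endpoint has an explicit anchor and 2.3.2.5 does not.

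The size is assumed throughout. This also stands. Nothing in the documents supports a 2% pre-dose rate, and at 0.5% the effect is small. The risk-difference interval in the table crosses zero only because 6% versus 2% happens to sit at the edge. With clean counts, the RR interval by the log method is already 0.96 to 9.36. A reader might infer that the missing rule costs the trial a significant safety finding; the figures do not show that.

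A reader might also infer that a kidney injury judged to be caused by the drug drops out of the endpoints, because 2.3.2.5 is limited to complications of hypertensive disease. The documents do not support this. Endpoint 2.3.2.6 covers adverse effects of furosemide, and such a case falls there even though kidney injury is not named. The cases are split by attributed cause, not lost. What remains is that the plan commits to no single kidney injury count by arm.

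**Conclusion.** The point holds, and it is minor. As written, 2.3.2.5 can count events that began before treatment, including features that qualified the woman for the trial. The effect is dilution of the relative risk plus extra noise. It should not be read as bias between the arms: allocation is randomized, blinded and stratified by severe features (5.2), so pre-dose events are balanced in expectation and the risk difference is essentially unchanged.

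The size depends on a pre-dose rate that the documents do not give. Under the 6% versus 2% assumption, a 0.5% rate takes the RR from 3.0 to 2.6 with a 6% wider interval. A 2% rate, which has no support in the documents, takes it to 2.0 with a 21% wider interval. The point concerns one secondary endpoint that the trial has little power to resolve anyway. The primary endpoint and the sample size are not affected.

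**What to change.** - Add to 2.3.2.5 that a complication counts only with onset or worsening after randomization.
- Define acute kidney injury relative to the last creatinine before the first dose, with the threshold fixed before unblinding.
- Report kidney injury by arm as one count whatever its attributed cause, so that cases are not divided between 2.3.2.5 and 2.3.2.6. Give the risk difference with a 95% confidence interval beside the relative risk.
- State per arm how many women had both a pre-dose and a post-dose creatinine.
- Complications found at readmission may be listed descriptively from the data already collected to 6 weeks (10.2), since dosing runs "for a total of 5 consecutive days during hospitalization and after discharge". They should not be folded into the creatinine-based count, because after discharge a creatinine will exist mainly for readmitted women.

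The cost is SAP wording and extraction of existing creatinine values, with no new visits or tests. The downside is fewer counted events and incomplete creatinine. Section 4.2 refers to "corresponding daily basic metabolic profiles", but 5.3 leaves laboratory tests to the clinical staff, so some women will lack one or both values.
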